1.5 RATIONALE FOR STUDY POPULATION

To assess safety, tolerability, and immunogenicity of the H1ssF_3928 vaccine, subjects 18-70 years of age will be enrolled. In the higher dose group, subjects will be stratified by age into four groups (Groups 2A-2D) to evaluate how the immune responses to the H1ssF_3928 vaccine vary based on age and the likelihood of exposure to different influenza strains.

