4.1.1 Inclusion Criteria

A subject must meet all of the following criteria:

1. Healthy adults between the ages of 18-70 years inclusive
2. Based on history and examination, in good general health and without history of any of the conditions listed in the exclusion criteria
3. Received at least one licensed influenza vaccine from 2014 to the present
4. Able and willing to complete the informed consent process
5. If enrolled in Group 1: Available for clinic visits for 52 weeks after enrollment and through an influenza season
6. If enrolled in Group 2A, 2B, 2C, or 2D: Available for clinic visits for 68 weeks after enrollment and through an influenza season
7. Willing to have blood samples collected, stored indefinitely, and used for research purposes
8. Able to provide proof of identity to the satisfaction of the study clinician completing the enrollment process
9. Physical examination and laboratory results without clinically significant findings and a Body Mass Index (BMI) ≤ 40 within the 28 days before enrollment

Laboratory Criteria within 28 days before enrollment

10. White blood cells (WBC) and differential either within institutional normal range or accompanied by the site Principal Investigator (PI) or designee approval
11. Total lymphocyte count ≥ 800 cells/mm³
12. Platelets = 125,000 – 500,000/mm³
13. Hemoglobin within institutional normal range

14. Serum iron either within institutional normal range or accompanied by the site PI or designee approval
15. Serum ferritin within institutional normal range or accompanied by the site PI or designee approval
16. Alanine aminotransferase (ALT) $\leq 1.25 \times$ institutional upper limit of normal (ULN)
17. Aspartate aminotransferase (AST) $\leq 1.25 \times$ institutional ULN
18. Alkaline phosphatase (ALP) $< 1.1 \times$ institutional ULN
19. Total bilirubin within institutional normal range
20. Serum creatinine $\leq 1.1 \times$ institutional ULN
21. Negative for HIV infection by an FDA-approved method of detection

Criteria applicable to women of childbearing potential:

22. Negative beta-human chorionic gonadotropin (β -HCG) pregnancy test (urine or serum) on the day of enrollment
23. Agrees to use an effective means of birth control from at least 21 days prior to enrollment through the end of the study

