4.1.2 Exclusion Criteria

A subject will be excluded if one or more of the following conditions apply:

1. Breast-feeding or planning to become pregnant during the study.

Subject has received any of the following substances:

2. More than 10 days of systemic immunosuppressive medications or cytotoxic medications within the 4 weeks prior to enrollment or any within the 14 days prior to enrollment
3. Blood products within 16 weeks prior to enrollment
4. Live attenuated vaccines within 4 weeks prior to enrollment
5. Inactivated vaccines within 2 weeks prior to enrollment
6. Investigational research agents within 4 weeks prior to enrollment or planning to receive investigational products while on the study
7. Current allergy treatment with allergen immunotherapy with antigen injections, unless on maintenance schedule
8. Current anti-TB prophylaxis or therapy
9. Previous investigational H1 influenza vaccine
10. Previous investigational ferritin-based vaccine
11. Receipt of a licensed influenza vaccine within 6 weeks before trial enrollment

Subject has a history of any of the following clinically significant conditions:

12. Serious reactions to vaccines that preclude receipt of study vaccinations as determined by the investigator
13. Hereditary angioedema, acquired angioedema, or idiopathic forms of angioedema

14. Asthma that is not well controlled
15. Diabetes mellitus (type I or II), with the exception of gestational diabetes
16. Thyroid disease that is not well controlled
17. Idiopathic urticaria within the past year
18. Autoimmune disease or immunodeficiency
19. Hypertension that is not well controlled (baseline systolic > 140 mmHg or diastolic > 90 mmHg)
20. Bleeding disorder diagnosed by a doctor (e.g. factor deficiency, coagulopathy, or platelet disorder requiring special precautions) or significant bruising or bleeding difficulties with IM injections or blood draws
21. Malignancy that is active or history of malignancy that is likely to recur during the period of the study.
22. Seizure disorder other than 1) febrile seizures, 2) seizures secondary to alcohol withdrawal more than 3 years ago, or 3) seizures that have not required treatment within the last 3 years
23. Asplenia, functional asplenia or any condition resulting in the absence or removal of the spleen
24. Guillain-Barré Syndrome

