6.3 SAMPLE SIZE AND ACCRUAL

Recruitment will target 53 healthy adult participants 18 to 70 years of age, though up to 70 participants may be enrolled if deemed necessary for safety or immunogenicity evaluations.

Enrollment will be spread over multiple groups. Group 1 will target 5 healthy adults 18 to 40 years of age. Groups 2A, 2B, 2C, and 2D will target 12 healthy adult participants each, with each study group corresponding to a different age range.

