6.4.4 Immunogenicity Analysis

The statistical analysis for immunogenicity will employ the intent-to-treat principle whereby all data from enrolled subjects will be analyzed according to the group assignment. However, if during immune assessment on stored samples, a subject is found to have a positive antibody response at baseline, the vaccine immune responses assessment for these subjects will not be included in the final immunogenicity analysis. If needed, a per-protocol analysis will be performed as secondary analysis where subjects will be analyzed according to their actual vaccination scheme if it is different from the assigned or up to the last visit in the study if there are early dropouts. The study is not designed to power the comparison in immune responses between vaccine dosages.

If assay data are qualitative (i.e., positive or negative) then analyses will be performed by tabulating the frequency of positive response for each assay at each time point that an assessment is performed. Binomial response rates will be presented with their corresponding exact 95% confidence interval estimates.

Some immunologic assays have underlying continuous or count-type readout that is often dichotomized into responder/non-responder categories. For these assays, graphical and tabular summaries of the underlying distributions will be made. These summaries may be performed on transformed data (e.g., log transformation) for ease of interpretation.

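### Section 6.4.4 drops baseline-antibody-positive subjects from the final immunogenicity analysis without defining positive, so the analysed population and its size are undetermined

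*Combined protocol and SAP*

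**What the plan says.** Section 6.4.4 names the intent-to-treat principle, under which "all data from enrolled subjects will be analyzed according to the group assignment". The next sentence makes an exception for the final immunogenicity analysis, if testing of stored samples shows that "a subject is found to have a positive antibody response at baseline, the vaccine immune responses assessment for these subjects will not be included". Neither this section nor any other says which assay, antigen or threshold makes a baseline sample positive.

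Four other parts of the plan bear on the rule:

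- **Who is enrolled.** Inclusion criterion 3 (Section 4.1.1) reads "Received at least one licensed influenza vaccine from 2014 to the present". The related exclusion (Section 4.1.2) is only "Receipt of a licensed influenza vaccine within 6 weeks before trial enrollment", so earlier exposure remains.
- **Why there are age groups.** Section 1.5 stratifies the higher-dose group "to evaluate how the immune responses to the H1ssF_3928 vaccine vary based on age and the likelihood of exposure to different influenza strains".
- **How many.** Section 6.3 states that "Groups 2A, 2B, 2C, and 2D will target 12 healthy adult participants each" and that "Group 1 will target 5 healthy adults 18 to 40 years of age". Section 6.3.2 applies the exact intervals of Table 6-2 to immune response rates at those full sizes.
- **Missing data.** Section 6.4.5 intends to use every available sample at each time point and treats gaps as missing completely at random.

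**The concern.** The exclusion depends on a baseline measurement that reflects past influenza exposure, and exposure history is one of the two things the age groups were set up to examine. Three consequences follow if any appreciable share of subjects is positive.

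The result would describe antibody-negative adults only, whereas the secondary objectives (Section 3.2) concern the antibody response of those vaccinated. The four age groups could lose different fractions, so that differences between them mix age with selection. And the intervals would be wider than Table 6-2 shows.

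A further problem holds at any rate. Because positive is undefined, two statisticians could apply the rule to the same data and analyse different subjects. The trial is open-label and baseline status is to be found on stored samples, and nothing in the text requires the cut-off to be fixed before post-vaccination results are seen.

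**Working it through.** **Inputs.** Group sizes 5 and 12, with 48 over Groups 2A-2D (Section 6.3); exact binomial 95% intervals (Table 6-2); Fisher power at 12 per group (Table 6-3). The baseline-positive rate q is not in the documents, so it is assumed, from 10% to 90%.

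**The plan's own figures.** Clopper-Pearson intervals reproduce every row of Table 6-2, for example 0/12: 0 to 0.265; 6/12: 0.211 to 0.789; 12/12: 0.735 to 1. Full enumeration of the two-sided Fisher test reproduces Table 6-3 to within one point (response rates 0.1 v 0.6: 63.9%, stated as 64). The plan does not state alpha; 0.05 was assumed. The tables are correct for the full group sizes and make no allowance for exclusions.

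**Subjects left.** If each subject is positive independently with probability q, the number kept from n is Binomial(n, 1 - q), with mean n(1 - q). A group of 12 is empty with probability q^12, and at least one of the four groups is empty with probability 1 - (1 - q^12)^4.

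| Assumed q | Expected kept of 12 | Chance 3 or fewer kept of 12 | Chance at least one of four groups empty | Expected kept of 5 | Expected kept of 48 |
|---|---|---|---|---|---|
| 10% | 10.8 | <0.1% | <0.1% | 4.5 | 43.2 |
| 25% | 9.0 | <0.1% | <0.1% | 3.75 | 36 |
| 50% | 6.0 | 7% | 0.1% | 2.5 | 24 |
| 80% | 2.4 | 79% | 25% | 1.0 | 9.6 |
| 90% | 1.2 | 97% | 73% | 0.5 | 4.8 |

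At q = 80%, for example, 12 x 0.2 = 2.4; 0.8^12 = 0.069; and 1 - (1 - 0.069)^4 = 0.25.

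**Precision left.** With about half responding, the exact 95% interval widens from 0.211-0.789 (6/12, width 0.58) to 0.137-0.788 (4/9, width 0.65) and 0.118-0.882 (3/6, width 0.76). If everyone analysed responds, the lower bound is 0.025^(1/n): 0.735 at 12/12, 0.664 at 9/9, 0.541 at 6/6 and 0.158 at 2/2. Fisher power for 0.1 v 0.6 falls from 63.9% (12 v 12) to 48.6% (9 v 9) and 14.1% (6 v 6).

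**Unequal loss.** As illustration only: if one age group were 25% positive and another 80%, the comparison would set an expected 9.0 subjects against 2.4, each selected by its own exposure history.

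**Enrolment to 70.** The ceiling allows 70 - 53 = 17 extra subjects. If all joined Group 2, 48 + 17 = 65 would be vaccinated, leaving 58.5, 48.75 and 32.5 at q = 10, 25 and 50%. The planned 48 can be restored up to about q = 1 - 48/65 = 26%, and not beyond.

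**The case against.** A reader might infer that baseline positivity will be common and the analysis nearly empty. The documents do not support that. They give no seropositivity figure. Section 1.1 describes stem-directed antibodies after infection as a small and less potent population, so weak antibody might not register in a pseudo-neutralization assay. Nor do they say that licensed vaccines induce stem antibody, so criterion 3 alone does not establish positivity. This part of the objection stands: a low rate is possible, and at 10% the loss is about one subject per group.

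A reader might also infer that the age comparison is biased. That is a risk and is not shown: Section 1.5 links exposure to age, but nothing says that positivity at the eventual cut-off differs by age, or in which direction. Restricting all groups to antibody-negative subjects is also a coherent question in itself. It is narrower than the one in Section 1.5, and it has no fixed meaning until positive is defined.

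The exception is openly declared, so it is not a hidden contradiction. It still means that the final analysis is not intent-to-treat as the preceding sentence describes it. Comparisons between age groups are exploratory, and Section 6.3.3 itself says they are not powered, so the fall in Fisher power takes away no promised inference.

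Nothing elsewhere cures the rule. The per-protocol analysis deals with vaccination actually received and with dropout. No analysis retains the excluded subjects. The enrolment ceiling carries no replacement rule for baseline-positive subjects. The missing-completely-at-random assumption does not describe removal based on baseline titre.

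**Conclusion.** The concern holds in this form: the plan removes baseline-positive subjects from the final immunogenicity analysis under an undefined criterion, in a previously vaccinated population aged up to 70 where some baseline stem antibody is plausible. The rule selects on a consequence of the exposure history under study, limits the conclusion to antibody-negative adults, and does not secure the denominators of 5 and 12.

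The size depends wholly on an unstated rate. The loss is small at 10%, can be offset by extra enrolment up to roughly 25%, halves the groups at 50% and is severe at 80% or more. These figures assume independent subjects and, in the table, one common rate across groups. The missing definition, and the lack of any analysis that keeps all subjects, matter at any rate. The primary safety objectives are untouched.

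**What to change.** In Section 6.4.4:

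- Include every subject with a Day 0 and a post-vaccination sample in the main immunogenicity analysis.
- Measure response against the subject's own Day 0 value, as a log change or a baseline-adjusted log titre. Define a responder by a fold rise set before the assays are run.
- Define baseline positivity by assay, antigen and cut-off, also in advance.
- Report results by baseline status, and keep the restriction to baseline-negative subjects only as a sensitivity analysis.

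No visit or sample changes: Appendix I already schedules Day 0 serum, and Section 4.2.5 requires blood to be drawn before injection. The cost is a protocol amendment with IRB submission (Section 9.1). One drawback remains: fold rises may be smaller in subjects with high baseline titres, so a simple fold-rise summary could understate their response. The baseline-adjusted estimate and the report by baseline status let a reader see this.

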6.4.5 Missing Data

Missing responses will be assumed to be missing completely at random. Analyses will include all samples available at each study time point. Based on experience from previous trials, we expect missing data to be rare. Regardless, in the event of missing data, we will report the occurrence and extent of missingness. We will also provide plausible explanations for the missingness mechanism, should such information be available.

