1. INTRODUCTION AND RATIONALE

1.1 BACKGROUND

Influenza virus causes seasonal epidemics and pandemics at irregular intervals that result in significant morbidity and mortality. According to the World Health Organization (WHO), the annual global attack rate of influenza is estimated to be 5%–10% in adults and 20%–30% in children; worldwide these annual epidemics result in about 3 to 5 million cases of severe illness and about 250,000 to 500,000 deaths [1]. The US Centers for Disease Control and Prevention (CDC) estimates that a pandemic influenza outbreak costs the United States between \$71 billion and \$167 billion without counting the financial impact on commerce and society [2].

Influenza is an enveloped, negative single-stranded (-ss) ribonucleic acid (RNA) virus that belongs to the family *Orthomyxoviridae*. Of the five genera of influenza circulating in nature, only influenza A and B are known to cause epidemics in humans [3].

Influenza A viruses consist of 8 RNA gene segments and are classified based on the antigenicity of their surface glycoproteins: hemagglutinin (HA) and neuraminidase (NA). There are 18 different HA subtypes (H1 through H18) and 11 NA subtypes known to exist, but only three HA subtypes (H1, H2, and H3) and two NA subtypes (N1 and N2) have caused significant human epidemics [4].

The HA is the predominant viral antigen target for antibody neutralization [5]. HA glycoprotein consists of a globular head domain (which is highly variant in structure between HA subtypes) and a stem domain (which is highly conserved across HA subtypes) [6]. Most of the antibodies produced by the immune system after infection recognize the head domain, whereas the stem domain is recognized by a small population of antibodies [7-9]. The anti-head antibodies are very potent but are strain-specific while the anti-stem antibodies are less potent and are cross-reactive across HA strains [10].

Influenza exhibits genetic flexibility and antigenic variability because of its ability to go through antigenic “drift” (the gradual accumulation of mutations over time) and antigenic “shift” (the replacement of the hemagglutinin gene by reassortment during contemporaneous infection of a host by more than one influenza strain). The emergence of new influenza strains through continuous mutation and reassortment of circulating virus diminishes the effectiveness of annual influenza vaccines [11, 12].

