4.2.1 Screening

Screening for this study will be completed through the VRC's screening protocol, VRC 500 (NIH 11-I-0164, NCT01375530). Subjects will be recruited through Institutional Review Board (IRB)-approved advertising. The evaluations and sample collections that will be included in screening are a medical history, physical exam, laboratory tests needed to confirm eligibility, and pregnancy test for females of reproductive potential.

If screening evaluations suggest a current concerning health condition or infection, such as hepatitis, then appropriate laboratory tests may be conducted to evaluate these conditions. Additional assessments of health may be conducted at screening based on clinical judgment. Screening evaluations for specific eligibility criteria (Section [4.1](#)) must be completed within the time interval specified prior to enrollment for the given parameter and may be repeated, as needed, to confirm eligibility. Research blood samples will be collected during screening;

although generally collected in the 28 days prior to enrollment; a particular interval of time prior to enrollment for collection of these samples is not required.

The informed consent form (ICF) will be reviewed and counseling related to pregnancy prevention will be provided.

Subjects who are not up to date on standard vaccinations may receive these, if available, during their participation in the screening protocol or at a later date during study participation. As part of the informed consent process, an Assessment of Understanding (AoU) is completed on the day the subject is scheduled to enroll prior to signing the VRC 321 protocol ICF. Incorrect answers will be explained to the subject, who will sign the ICF only after the study clinician is satisfied with the subject's understanding of the study.

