4.2.12 Concomitant Medications

Only routine prescription medications will be entered in the database at the time of enrollment. Subsequently, the only concomitant medications that will be recorded or updated in the database are those associated with an AE requiring expedited reporting or the development of a new chronic condition requiring ongoing medical management. Anti-viral medications taken during influenza or influenza-like illnesses will be recorded in the database. Receipt of a FDA-approved vaccine at any time during the study will be recorded in the database (clinicians should work with subjects regarding the timing of licensed vaccines relative to study injection). Otherwise, concomitant medications taken throughout the study will be recorded in the subject's study chart and general medical record for general medical documentation but will not be recorded in the database.

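### The immunogenicity analysis has no rule for samples taken after an on-study licensed influenza vaccine or PCR-confirmed influenza, so they count as study-vaccine response; the risk lies mainly from Week 16 on

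*Combined protocol and SAP*

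**What the plan says.** Section 6.4.4 applies an intent-to-treat principle in which "all data from enrolled subjects will be analyzed according to the group assignment". It makes one exception: where "a subject is found to have a positive antibody response at baseline", that subject's responses are left out of the final immunogenicity analysis. An optional per-protocol analysis is described in which "subjects will be analyzed according to their actual vaccination scheme if it is different from the assigned", or in which early dropouts are followed to their last visit. Section 6.4.5 adds that "Analyses will include all samples available at each study time point".

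On exposure to other influenza antigens:

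- Section 4.1.2 excludes "Receipt of a licensed influenza vaccine within 6 weeks before trial enrollment". This covers the time before Day 0 only.
- Section 4.2.1 lets subjects who are behind on standard vaccinations receive them during screening "or at a later date during study participation".
- Section 4.2.12 states that "Receipt of a FDA-approved vaccine at any time during the study will be recorded in the database". It asks clinicians to discuss with subjects when licensed vaccines fall relative to the study injections, but sets no interval.
- Section 5.1 provides for a nasopharyngeal swab and PCR in subjects who meet the definition of influenza-like illness, and for recording confirmed cases.
- Section 4.2.7 requires follow-up to span an influenza season.

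The principal immunogenicity measure (Section 6.2.2) is HA-stem specific antibody by pseudo-neutralization, at baseline and Week 2 in all groups and also at Weeks 16 and 18 in Groups 2A-2D. Section 1.6 names two weeks after the first injection as the primary immunogenicity time point and plans the same assay on stored samples from the whole study.

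**The concern.** The plan treats earlier influenza antigen exposure as a problem before Day 0, through the six-week exclusion and the removal of baseline-positive subjects. It has no counterpart after Day 0. Yet exposure after Day 0 is foreseeable: inclusion criterion 3 requires every subject to have had a licensed influenza vaccine since 2014, and follow-up spans a season by design. Section 1.1 describes anti-stem antibodies as reacting across HA strains, so a stem-specific assay does not by itself show which exposure caused a rise. With no control arm, a seasonal rise cannot be subtracted.

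A stated objective is affected. Section 3.2 covers two weeks after each 60 mcg injection, and Section 6.4.6 allows those results to inform decisions on future trials. The study is also open-label, so without a rule the choice to keep or drop an exposed subject could be made after titres are known.

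**Working it through.** **1. The plan's own figures.** Table 6-2 gives exact 95% intervals, and Section 6.3.2 applies them to response rates. The Clopper-Pearson limits are the 0.025 quantile of Beta(x, n−x+1) and the 0.975 quantile of Beta(x+1, n−x). They reproduce every entry for n=5 and n=12; the largest difference is 0.0004. Tables 6-1 and 6-3 also reproduce (Table 6-3 with two-sided alpha 0.05, which is assumed because it is not stated). The point is therefore not an arithmetic error.

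**2. What happens to a post-exposure sample.** Take a Group 2 subject, negative at baseline, who receives a licensed influenza vaccine in Week 10 and gives a sample in Week 16. The baseline exclusion does not apply. The per-protocol rule does not apply, because the study vaccination scheme is as assigned and there is no dropout. Sections 6.4.4 and 6.4.5 then include the sample under the assigned group. The same holds after PCR-confirmed influenza.

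**3. Expected infections.** Section 1.1 says "the annual global attack rate of influenza is estimated to be" 5%–10% in adults. Spreading this evenly over the year (an assumption), the share infected by week w is 1 − (1 − a)^(w/52), with a the annual rate. It is multiplied by 48 for Groups 2A-2D combined.

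| By | a = 5% | a = 10% | Expected of 48 |
|---|---|---|---|
| Week 2 | 0.2% | 0.4% | 0.1–0.2 |
| Week 18 | 1.8% | 3.6% | 0.8–1.7 |
| Week 68 | 6.5% | 12.9% | 3.1–6.2 |

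Windows that fall inside an influenza season would be higher. PCR is done only in subjects with influenza-like illness, so not every infection would be detected.

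**4. Effect on a response rate.** Let p be the true response rate to the study vaccine, q the share exposed before the sample, and r the chance that an exposure gives a positive stem result. If exposure is independent of vaccine response, the observed rate is p + (1 − p)·q·r. Uptake of licensed vaccine is not in the documents, so q and r are assumptions; r = 1 is the upper limit. With p = 0.20:

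| q | r = 0.25 | r = 1 |
|---|---|---|
| 0.10 | 0.22 | 0.28 |
| 0.25 | 0.25 | 0.40 |
| 0.50 | 0.30 | 0.60 |

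For q = 0.25: 0.20 + 0.80 × 0.25 × 0.25 = 0.25, and 0.20 + 0.80 × 0.25 × 1 = 0.40. Infection alone by Week 18 (q at most 0.036 under step 3) gives at most 0.20 + 0.80 × 0.036 ≈ 0.23. Anything larger by Week 18 would have to come from licensed vaccination or from a window inside a season.

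**5. Sensitivity of a group of 12.** One extra responder adds 1/12, or 8.3 percentage points. In Table 6-2 that moves 2/12 (0.021–0.484) to 3/12 (0.055–0.572).

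**6. Reference for Week 18.** Section 4.2.5 requires blood to be drawn before vaccination, so the Week 16 sample precedes the second injection. Read against Day 0, the Week 18 value carries any exposure over 18 weeks. Read against Week 16, only exposure close to or after Week 16 can inflate the rise, and an earlier exposure could lower it by raising the reference. The plan does not say which reference is used.

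**The case against.** Analysing all data by assigned group is a legitimate choice, and the sentence in Section 6.4.5 concerns missing data, not intercurrent exposure. That is fair, but Section 6.4.4 leads to the same result without it.

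Several features limit the risk, and all of them stand. The primary immunogenicity time point is two weeks after the first injection, where fewer than one infection is expected among 48. Section 4.2.12 asks clinicians to work on the timing of licensed vaccines. The assay is stem-specific, and Section 1.1 says most antibody after infection targets the head, so an exposure need not give a positive result. All subjects have had licensed influenza vaccine, yet those analysed must be negative at baseline, which also argues against assuming that every exposure converts. Assays after Week 18 are additional assessments, not listed secondary endpoints.

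A reader might infer that the reported titres are known to be inflated by a material amount, or that the age comparison is distorted. The documents do not support either. They give no uptake, no enrolment season, no effect of exposure on stem titre and no difference in exposure between age groups. Section 6.3.3 also treats the age comparison as exploratory and says it is not powered.

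A reader might also infer that exposed samples must be dropped from the main estimate. That goes too far. Removing samples after infection conditions on an event after vaccination: if poor responders are more often infected, dropping them raises the estimate. It could also leave few late samples. At 50% exposure, for example, 12 × 0.50 = 6 subjects per group would remain.

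**Conclusion.** The concern holds as a gap in the analysis rules. Followed literally, Sections 6.4.4 and 6.4.5 credit the study vaccine with stem-antibody rises that follow a recorded licensed influenza vaccine or confirmed influenza, and nothing in the design separates the two sources.

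Week 2 is largely spared, though not fully protected, because the timing guidance sets no interval. The exposed results are Week 16 and Week 18 values read against Day 0, and the later stored-sample assessments. The size cannot be fixed from the documents. The range 0.25 to 0.40 for a true rate of 0.20 rests on an assumed 25% exposure and an assumed 25% to 100% conversion; it shows what is possible and is not an estimate of what will occur. The gap calls for a second, pre-specified analysis. It does not show that the planned one is invalid.

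**What to change.** Add to Section 6.4.4:

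- A pre-specified analysis of response rates and titre summaries that censors each subject's samples from the date of any on-study licensed influenza vaccine or PCR-confirmed influenza. Report it beside the all-samples analysis for every visit after Day 0.
- A listing of affected subjects by group and visit, with their samples flagged in plots.
- A statement of whether the Week 18 response is measured against Day 0 or Week 16.

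The cost is wording and one more set of tables; vaccine receipt and influenza PCR results are already collected. The drawbacks are fewer samples at late visits in the censored analysis and possible selection from censoring on infection. The missing-completely-at-random assumption in Section 6.4.5 should not be carried over to censored samples without comment. Showing both analyses makes the selection visible. Neither analysis deals with infections that were never swabbed, and the report should say so.
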